4.4. Subject Discontinuation or Withdrawal

Subjects will receive study treatment until protocol-specified study completion or treatment discontinuation for one of the reasons listed below. However, subjects may discontinue study treatment or withdraw their consent to participate in the study at any time without prejudice. In the event that a subject discontinues from the study prematurely, and unless consent is withdrawn, all efforts must be made to collect efficacy and safety data and to complete the Early Termination Visit (Visit 8). The following conditions require subject discontinuation from all study treatment:

- At their own request
- If a subject experiences an AE that is deemed related to treatment with PTC518 and in the investigator's or PTC's medical judgment continuation of treatment would be detrimental to the subject
- At the specific request of a regulatory agency or DSMB for termination of treatment of an individual subject or all subjects under the protocol
- Subject participation in another clinical study using an investigational agent or investigational medical device
- Refusal of sexually active fertile subjects (excluding female subjects who have been sterilized) to use medically accepted methods of contraception
- If a subject becomes pregnant
- Significant noncompliance with the protocol in the opinion of the investigator or PTC
- Any situation in which the investigator determines that the subject should not continue in the study

The date PTC518 is discontinued and the reason for discontinuation will be recorded in the source documents and in the electronic case report form (eCRF). The medical monitor (and designee) must be informed via email when a subject discontinues study drug.

When PTC518 is discontinued, the investigator is expected to perform all the evaluations according to the subject's original schedule and as required at the Early Termination Visit and any additional evaluations that may be necessary to ensure that the subject is free of untoward effects.

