9.3.3.2. Analysis of Secondary Endpoints

The key secondary endpoint (change from baseline in caudate volume as assessed via vMRI at Month 12) will be analyzed by a mixed model repeated measures (MMRM) model using all available vMRI data up to the Month 12 Visit. The model will include fixed effects for treatment, baseline vMRI, and disease stage (by PIN_{HD} bin for Stage 2 only and by TFC for Mild Stage 3 only). The intercept and time of collection will be included as a random effect nested within subjects. The unstructured covariance matrix will be used in the model. The rate of changes will be compared between treatments and the least squares (LS) mean differences at Month 12 will also be provided.

For change from baseline in cUHDRS, a MMRM analysis (repeat at visit) will be performed using all data collected up to 12 months. The model will use treatment group, visits (categorical), treatment by-visit interaction, disease stage as fixed factors, CAG, age, and CAG by age interaction as covariates. The LS mean estimates for the change from Month 12, the difference between pairwise comparison with placebo, confidence intervals, and 2-sided p value will be presented. A similar model will be used for UHDRS sub-scores and PBA-s. Rate of changes in these scores will also be explored.

For by disease stage analyses, PIN_{HD} category (0.180 to 0.679, 0.680 to 1.520, or 1.521 to 4.930) will be used as a fixed factor for Stage 2 only, and TFC score (11, 12, or 13) will be used as a fixed factor for Mild Stage 3 only.

A repeated measure analysis model, similar to the analysis model used for blood tHTT protein, will be used for blood and CSF mHTT protein. Dose-response relationships will be explored and a by-visit summary of blood tHTT and blood and CSF mHTT protein will be displayed.

An analysis of covariance model with dose and Baseline in the model will be used to analyze change from Baseline to Month 12 in mHTT protein (in blood and CSF). Nominal p values and 95% confidence interval for each pairwise comparison will be calculated.

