3. GENERAL CONSIDERATIONS

3.1. Definition of Estimand

The primary estimand of the study is intended to provide a population level estimate of treatment effect in terms of the change from baseline in blood tHTT protein at Month 3, by a hypothetical strategy. The primary analysis will be based on ITT population, aiming to answer the research question: what is the change from baseline in blood tHTT protein at Month 3 for all randomized subjects during their treatment period, defined as the time from randomization until 30 days after they stop the treatment. [Table 1](#) lists all estimands in the study.

Table 1: Study Endpoints and Estimands

Endpoint	Population	Variable	Intercurrent events	Population level summary	Analysis
Blood tHTT protein	Stage 2 and Mild Stage 3 HD subjects aged 25 years and older as defined by the protocol I/E criteria (ITT Population)	Change from baseline in blood tHTT protein at Month 3	Discontinuation of study treatment (due to any reason); data after the last dose of study drug + 30 days will be excluded.	Treatment difference and corresponding 95% confidence interval (CI) between each PTC518 dose group and placebo group in the change from baseline in blood tHTT protein at Month 3 will be estimated using a mixed model repeated measures (MMRM).	Primary analysis for primary endpoint
Blood tHTT protein	Stage 2 and Mild Stage 3 HD subjects aged 25 years and older as defined by the protocol I/E criteria, with no major protocol deviations which may affect treatment efficacy measurements (PP Population)	Change from baseline in blood tHTT protein at Month 3	Discontinuation of study treatment (due to any reason); data after the last dose of study drug + 30 days will be excluded.	Same as primary analysis for primary efficacy endpoint	Sensitivity analysis for primary endpoint
Blood tHTT protein	Stage 2 and Mild Stage 3 HD subjects aged 25 years and older as defined by the protocol I/E criteria (ITT Population)	Change from baseline in blood tHTT protein at Month 3 based on the results from	Discontinuation of study treatment (due to any reason); data after the last dose of study drug + 30 days will be excluded.	Same as primary analysis for primary efficacy endpoint	Sensitivity analysis for primary endpoint

PTC518-CNS-002-HD
Statistical Analysis Plan

Endpoint	Population	Variable	Intercurrent events	Population level summary	Analysis
		complete run (see definition in Section 5.2.3)			

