Blood tHTT protein	Completers of Stage 2 and Mild Stage 3 HD subjects aged 25 years and older as defined by the protocol I/E criteria (ITT Population completers)	Change from baseline in blood tHTT protein at Month 3	Discontinuation of study treatment (due to any reason); data after the last dose of study drug + 30 days will be excluded.	Same as primary analysis for primary efficacy endpoint	Sensitivity analysis for primary endpoint
Blood tHTT protein	Stage 2 and Mild Stage 3 HD subjects aged 25 years and older as defined by the protocol I/E criteria (ITT Population)	Change from baseline in blood tHTT protein at Month 3	Discontinuation of study treatment (due to any reason); data after the last dose of study drug + 30 days will be excluded.	Treatment difference and corresponding 95% CI between each PTC518 dose group and placebo group in the change from baseline in blood tHTT protein at Month 3 will be estimated using a MMRM model, with missing data imputed using a control-based method.	Sensitivity analysis for primary endpoint
Caudate volume via vMRI	Stage 2 and Mild Stage 3 HD subjects aged 25 years and older as defined by the protocol I/E criteria (ITT Population)	Percent change from baseline in caudate volume as assessed via vMRI at Month 12	Discontinuation of study treatment (due to any reason); data after the last dose of study drug + 30 days will be excluded.	Treatment difference and corresponding 95% CI between each PTC518 dose group and placebo group in the percent change from baseline in caudate volume at Month 12 will be estimated using a MMRM model.	Analysis of key secondary endpoint
cUHDRS	Stage 2 and Mild Stage 3 HD subjects aged 25 years and older as defined by the protocol I/E criteria (ITT Population)	Change from baseline in cUHDRS scores at Month 12	Discontinuation of study treatment (due to any reason); data after the last dose of study drug + 30 days will be excluded.	Treatment difference and corresponding 95% CI between each PTC518 dose group and placebo group in the change from baseline in cUHDRS scores at Month 12 will be	Analysis of secondary endpoint

Endpoint	Population	Variable	Intercurrent events	Population level summary	Analysis
				estimated using an analysis of covariance (ANCOVA) model.	

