3.4.6. Study Analysis Visit

Study analysis visits during the study will be derived as listed in [Table 2](#), based on study days from the randomization date. This window applies to scheduled, unscheduled, or early termination visits. The analysis visit number for each visit, including scheduled, unscheduled, repeat, and early termination/end of study visits, will be re-mapped. Study analysis visits will be used in all by-visit summaries for both efficacy and safety assessments wherever appropriate.

Table 2: Analysis Visit Windows

Analysis Visit	Target Study Day	Analysis Window (Study Day Range)
Visit 3 (Month 1)	30	16-45
Visit 4 (Month 2)	60	46-75
Visit 5 (Month 3)	90	76-120
Visit 6 (Month 6)	180	151-210
Visit 7 (Month 9)	270	241-300
Visit 8 (Month 12)	360	331- (last dose of study drug + 30 days)

For a given subject, if multiple assessments are within the same analysis window, the assessment at the scheduled visit will be used for the analysis; if the scheduled assessment is not available, the one closest to the scheduled study day and with non-missing value will be used for the analysis at that visit. In case of equal number of days to the scheduled visit date, the later assessment with non-missing value will be used for the analysis at that visit. In summary, the assessment to be used for the analysis is determined by the following order:

- 1) The assessment at the scheduled visit
- 2) The assessment closest to the target study day
- 3) The latter assessment, if ≥ 2 observations are equally close to the target study day

Any assessments occurring beyond the last dose of study drug + 30 days will be excluded from the analysis.

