3.4.8. Missing Data

All available data will be included in the data analysis and presented in data listings and tabulations. Missing data will not be imputed for summaries of all safety endpoints and by-visit summaries of all the PD parameters.

For the primary analysis and secondary analyses, where a mixed model repeated measures (MMRM) model will be used, the missing data will be implicitly imputed assuming the missing assessments are missing at random (MAR).

To further assess the influence of missing data for the primary analysis, missing primary endpoint will be imputed using a controlled-based multiple imputation (MI) ([Rubin 1987](#), [Ouyang 2017](#)) method under an assumption of missing not at random (MNAR).

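### For caudate volume and cUHDRS, the SAP excludes assessments made more than 30 days after last dose, where the protocol uses all data to Month 12, and does not declare the change

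*SAP*

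**What the plan says.** **Protocol.** Section 4.4 says that once drug is stopped, "the investigator is expected to perform all the evaluations according to the subject's original schedule and as required at the Early Termination Visit". Section 9.3.3.2 analyses caudate volume, the key secondary endpoint, with a "mixed model repeated measures (MMRM) model using all available vMRI data up to the Month 12 Visit". It takes cUHDRS data through 12 months in a repeated-measures model. Neither plan has a limit tied to the last dose.

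**SAP.** Section 3.4.6 closes with "Any assessments occurring beyond the last dose of study drug + 30 days will be excluded from the analysis". Table 2 in that section gives the Month 12 window as "331- (last dose of study drug + 30 days", so the window opens on Day 331 and has no fixed end. In Table 1 (section 3.1), caudate volume and cUHDRS have one row each, and both state "Discontinuation of study treatment (due to any reason); data after the last dose of study drug + 30 days will be excluded". The text above that table targets the primary estimand, blood tHTT at Month 3, "by a hypothetical strategy". It names no strategy for any other endpoint.

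Section 5.3 analyses cUHDRS with a single-visit ANCOVA at Month 12. It analyses caudate volume with a random intercept and slope in continuous time. The sensitivity analyses in 5.2 concern Month 3 tHTT only. The one sensitivity analysis of a secondary endpoint concerns CSF mHTT outliers and keeps the same cut-off. Section 3.4.8 states in general terms that "All available data will be included in the data analysis and presented in data listings and tabulations". Section 3.5 reports no departure from the protocol's analysis.

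**The concern.** For a blood marker of drug action at Month 3, leaving out off-drug values is easy to justify, and the SAP declares the strategy. Caudate volume and cUHDRS are different: they measure disease progression over a year, and their analyses are labelled ITT. Under the cut-off each becomes an on-treatment comparison. The SAP gives no reason for this and does not list it as a change.

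The result for the key secondary endpoint, and for the only clinical secondary endpoint, then rests on an assumption: that subjects who stopped would have followed the same course as similar subjects still on drug. Where Month 12 values exist after stopping, they bear on how those subjects actually fared, and no planned analysis of either endpoint uses them.

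**Working it through.** **The plan's own sample size.** The normal-approximation formula for two equal groups is n = 2 × ((1.960 + 1.036) / 0.85)² = 24.85 per group, close to the stated 24. This sizes Month 3 tHTT only and is used here just to set the arm sizes. The ceiling also checks: 2 × (3 × 24 + 36 + 18) = 252.

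**Who has a usable Month 12 value.** Let D be the study day of last dose. The Month 12 window runs from Day 331 to D + 30.
- The window is empty when D + 30 < 331, that is, when D is before Day 301.
- Around the SAP target of Day 360, the protocol's ±7 days gives visits on Days 353-367. A visit on Day 353 counts only if D ≥ 323, on Day 360 only if D ≥ 330, and on Day 367 only if D ≥ 337.
- So for D from 301 to 336, inclusion depends on the date of the visit. Within that range, for D from 301 to 322, no visit on Days 353-367 qualifies. An early termination visit on or after Day 331 and within 30 days of last dose would still be mapped to Month 12.
- For D ≥ 337, any visit in the protocol window counts.

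**Effect on cUHDRS.** The composite needs the Stroop word reading score. The protocol's schedule collects only the SDMT from the cognitive part at Visits 3 to 7, so a full composite exists only at Baseline and at Visit 8 or early termination. With D before Day 301, no permitted assessment falls in the Month 12 window, and the subject contributes nothing to the ANCOVA.

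**Effect on caudate volume.** Scans are scheduled at Baseline, Month 3 and Month 12 or early termination. The model uses actual scan dates, so the closing sentence of 3.4.6 and the Table 1 row remove late scans, not the Table 2 window. An early stopper still enters through the Month 3 scan and any early termination scan within 30 days of last dose. The model carries that course to Month 12 under missing at random. A Month 12 scan done later than D + 30 is left out.

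**Numbers at risk.** With 144 subjects in the 5 mg and 10 mg parts at 2:1, each active arm has 144 × (2/3) / 2 = 48 and pooled placebo has 144 / 3 = 48. No discontinuation rate is given, so I assume a proportion d of 5-20% stopping early enough to lose Month 12.
- Subjects per arm: 48 × 0.05 = 2.4 to 48 × 0.20 = 9.6, leaving 45.6 to 38.4.
- Standard error ratio for a single-visit analysis, 1 / √(1 − d): 1.03 at 5%, 1.05 at 10%, 1.12 at 20%.
- Difference detectable with 80% power, 48 v 48: 0.572 SD with everyone, 0.587-0.639 SD after the loss. With 72 on placebo: 0.522 SD, then 0.536-0.584 SD.

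The last two lines describe cUHDRS. They do not describe the caudate model, which keeps earlier scans.

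**Illustration of a shift.** Suppose stoppers end 0.5 SD worse than the model assumes, with 5% stopping on placebo and 10-20% on active. The on-treatment difference then exceeds the treatment-policy difference by (0.10 − 0.05) × 0.5 = 0.025 SD to (0.20 − 0.05) × 0.5 = 0.075 SD. With equal stop rates the figure is zero, and with more stopping on placebo it changes sign.

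**The case against.** The strongest reply is that few such Month 12 values may exist. Protocol 4.4 asks both for the original schedule and for the Early Termination evaluations. The Schedule of Assessments merges Month 12, end of treatment and early termination into one Visit 8 column, and the safety follow-up visits after it include neither vMRI nor UHDRS. On that reading, a stopper's last scan and UHDRS are taken at early termination and there is nothing later to exclude. This stands as a limit on the numbers. It does not remove the instruction to continue on schedule, nor the SAP's rule for any values that result.

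A hypothetical strategy is also legitimate, Table 1 discloses the cut-off for each endpoint, and this is a Phase 2a study whose secondary endpoints carry nominal p-values. All of that is true, and it is why the on-treatment analysis should stay. It does not explain why the strategy is argued only for tHTT, or why SAP 3.5 omits the change.

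A reader might infer more than the documents support:
- *Every stopper's observed Month 12 value is thrown away and stoppers vanish from both analyses.* Attendance after stopping is not assured, stoppers remain in the caudate model through earlier scans, and some who stop after Day 300 still have an eligible visit.
- *The rule biases the results in favour of drug.* No stop rates by arm or outcomes after stopping are given, so direction and size are open.
- *Visits after stopping serve no purpose.* They also collect safety data, and all adverse events are listed.
- *SAP 3.4.8 flatly contradicts the rule.* It is a general sentence set against a specific exclusion. The firmer conflict is with Protocol 9.3.3.2.

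**Conclusion.** The concern holds as a mismatch between protocol and SAP with a practical consequence. The SAP narrows the data for caudate volume and cUHDRS to the period up to 30 days after last dose, offers no other analysis of either, and reports no change. The loss of Month 12 information is complete for cUHDRS when last dose is before Day 301. For caudate volume it is partial, because earlier scans remain.

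The text conflict and the Day 301 limit need no assumption. The size does: 2-10 subjects per arm is an upper bound that assumes 5-20% stopping and full attendance at Month 12 afterwards. The 3-12% larger standard error applies to cUHDRS alone, and the 0.025-0.075 SD shift is only an illustration. The effect may well be modest, so this is a change that should be made and not one on which the trial depends.

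**What to change.** - Keep the Table 1 on-treatment analyses as they are.
- Add, for caudate volume and cUHDRS, one prespecified treatment-policy analysis with the same models. It should use every assessment up to Month 12 whether or not the subject was still on drug, and end at any first dose in PTC518-CNS-004-HD.
- For that analysis, replace the Table 2 upper bound with a fixed study day, for example Days 331-390. This continues the spacing of the Month 6 and Month 9 windows (151-210 and 241-300). Also exempt the analysis from the closing sentence of 3.4.6. Both changes are needed: if only the sentence is changed, Table 2 still closes Month 12 at 30 days after last dose and the cUHDRS ANCOVA still loses these values.
- Add the matching rows to Table 1.
- List the restriction to 30 days after last dose in SAP 3.5 as a change from Protocol 9.3.3.2.

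The cost is SAP wording and two more model runs on data the protocol already expects to be collected. The added estimate may be somewhat diluted by time off drug. It also does not supply values for subjects who never attend Month 12; those stay missing under each model's own assumption.

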3.4.7. Multiplicity Control

For the primary efficacy analysis, to control the family-wise Type I error at the 0.05 level, a fixed sequence (hierarchical) testing procedure will be employed, where the treatment effect between PTC518 10 mg versus placebo will be tested first at the significance level of 0.05 (2-sided) and if p-value < 0.05 , the treatment effect between PTC518 5 mg versus placebo will be tested at the significance level of 0.05 (2-sided).

The secondary and exploratory efficacy endpoints will be analyzed at the significance level of

0.05 (2-sided) without multiplicity adjustment.

3.4.8. Missing Data

All available data will be included in the data analysis and presented in data listings and tabulations. Missing data will not be imputed for summaries of all safety endpoints and by-visit summaries of all the PD parameters.

For the primary analysis and secondary analyses, where a mixed model repeated measures (MMRM) model will be used, the missing data will be implicitly imputed assuming the missing assessments are missing at random (MAR).

To further assess the influence of missing data for the primary analysis, missing primary endpoint will be imputed using a controlled-based multiple imputation (MI) ([Rubin 1987](#), [Ouyang 2017](#)) method under an assumption of missing not at random (MNAR).

3.5. Changes to Protocol Specified Analysis

There are no changes to the planned analysis.

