2.7. Secondary Endpoints

- Change from Baseline in caudate volume as assessed via vMRI at Month 12 (key secondary)
- Change from Baseline in cUHDRS scores at Month 12

- Change from Baseline in blood tHTT protein at Month 12
- Change from Baseline in CSF mHTT protein at Month 12
- Change from Baseline in blood mHTT protein at Month 12

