9.6. Missing Data

Missing data will not be imputed for summaries for all safety endpoints and for by-visit summaries for all the PD parameters including tHTT protein (in blood).

For the primary analysis of the primary endpoint, MMRM model will be used on the available data assuming the missing assessments are missing at random. Missing data will be imputed using the multiple imputation procedure ([Rubin 1987](#), [Ouyang 2017](#)) to further assess the influence of missing primary endpoint data and details of the method will be provided in the SAP. Briefly, these methodologies will include multiple imputation under an assumption of missing not at random and tipping-point analyses to explore how extreme the difference between randomized treatments would have to be among subjects with missing data to overwhelm the treatment effect obtained in the primary. In these analyses, the multiple imputation approach will be expanded to allow for varying impact of missing data by incorporating a shift parameter in the imputation model. The range of values for the shift parameter will explore the varying missing data assumptions, including the scenario where the imputation model is completely based on the control group (ie, control-based imputation).

More details of missing data handling will be provided in the SAP.

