1. INTRODUCTION AND OVERVIEW

The objective of this Statistical Analysis Plan (SAP) is to outline the procedures and statistical methods that will be employed to support the final reporting of Study PTC518-CNS-002-HD (PIVOT-HD) after the database lock for the double-blind treatment period. The statistical methods described here are based on Final Protocol Version 6.0, dated 05 October 2023. All decisions concerning the final analysis will be made before the database lock for the double-blind treatment period and the treatment unblinding and will be documented in this SAP.

This study will include a database lock for the double-blind treatment period and a final database lock. The database lock for the double-blind treatment period will occur after all subjects complete 12 months of treatment (Visit 8). The data collected during the double-blind treatment period will be included in the analysis and reported in the Clinical Study Report (CSR).

Specifically, the study assessments up to 30 days (i.e., 1-month safety follow-up) after 12 months of treatment (Visit 8) will be included in the double-blind treatment period. The final database lock will take place after all subjects have completed the study. Listings for the additional data collected beyond the double-blind treatment period will be provided and reported after the final database lock.

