3.3. Interim Analysis

An interim analysis was conducted in June 2023 to confirm the PK and PD expectations and to evaluate safety after approximately 36 subjects in Stage 2 have completed 12 weeks of treatment. Subsequently, in June 2024, an update of interim analysis was conducted when these subjects completed 12 months of treatment. The interim analyses included only descriptive summaries of PK, PD, clinical efficacy and safety endpoints. Since the interim analyses followed the same procedures as the DSMB, the analysis details were outlined in the DSMB SAP.

An independent analysis team conducted the unblinded analysis. Only summary level results were shared with the PTC study team. The study has maintained double-blinding for investigators and the sponsor study team at a subject level until after the database is locked.

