5.3. Secondary Endpoints Analysis

Key Secondary Endpoint Analysis

The percent change from baseline in caudate volume as assessed via vMRI at Month 12 is the key secondary endpoint.

A MMRM model will be used to compare each PTC518 dose group with placebo group for the percent change from baseline in caudate volume as assessed via vMRI at Month 12. The response variable is the percent change from baseline in caudate volume. The model will include fixed effects for treatment, disease stage (by PINHD bin for Stage 2 only and by TFC for Mild Stage 3 only) with baseline caudate volume as a covariate. The time and time by treatment interactions will be included in the model where time is defined as: date of caudate assessment – date of randomization + 1. The intercept and time of collection will be included as a random effect nested within subjects.

The unstructured covariance matrix will be used in the model. If the model does not converge under the unstructured covariance matrix, the Variance Component covariance matrix will be used/. If the model still does not converge, the random effect will be excluded. The treatment effect and treatment difference will be estimated by the LS means and the difference in LS means, along with their SE and with 95% CIs, and the nominal p-values (2-sided) for each pairwise comparison (PTC518 vs. placebo) will be provided.

The caudate volume (left, right, and total [left + right]) and percent change from baseline will be summarized descriptively by treatment group for each visit.

Other Secondary Endpoints Analysis

Other secondary endpoints include:

- Change from baseline in cUHDRS scores at Month 12

An ANCOVA model will be performed to compare each dose group with placebo group for the change from baseline in cUHDRS at Month 12. The model will include treatment group as the independent variable and baseline cUHDRS, disease stage, CAG, age, CAG by age interaction as covariates. The treatment effect and treatment difference will be estimated by the LS means and the difference in LS means, along with their SE and with 95% CIs, and the nominal p-values (2-sided) for each pairwise comparison (PTC518 vs. placebo) will be provided.

- Change from baseline in blood tHTT protein at Month 12

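### SAP 3.5 declares no changes from the protocol, yet the scale of the key secondary endpoint, the tipping-point analysis and several other analyses differ from Protocol 6.0

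*SAP*

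**What the plan says.** SAP section 1 fixes the point of comparison: "The statistical methods described here are based on Final Protocol Version 6.0, dated 05 October 2023". SAP 3.5 then says, in full, "There are no changes to the planned analysis".

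Protocol 2.7 defines the key secondary endpoint as "Change from Baseline in caudate volume as assessed via vMRI at Month 12 (key secondary"), and Protocol 9.3.3.2 and SAP 1.3.2 agree. SAP 5.3 says instead: "The percent change from baseline in caudate volume as assessed via vMRI at Month 12 is the key secondary endpoint". SAP Table 1 also has percent change.

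For the same endpoint, Protocol 9.3.3.2 adds: "The rate of changes will be compared between treatments". For missing primary data, Protocol 9.6 commits to "tipping-point analyses to explore how extreme the difference between randomized treatments would have to be".

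On timing, SAP 3.3 reports: "An interim analysis was conducted in June 2023 to confirm the PK and PD expectations and to evaluate safety". It adds that "in June 2024, an update of interim analysis was conducted when these subjects completed 12 months of treatment". An independent team ran both analyses unblinded, and the sponsor's study team received summary-level results. SAP section 8 dates version 1.0, the initial release, 17 March 2025.

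**The concern.** Section 3.5 is where a reader looks to learn which analyses are the protocol's own and which were settled later. If it says that nothing changed, the percent-change caudate result and the altered CSF mHTT analysis will be read as analyses set by the protocol. The SAP also contradicts itself on the key secondary endpoint, because 1.3.2 and 5.3 name different variables.

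Two consequences go beyond labelling. The protocol's key secondary variable would never be modelled, so the report would hold no estimate, interval or p value for it. The analysis meant to show how much departure from missing-at-random the primary result can bear would not be done.

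**Working it through.** No number stands behind the declaration, so there is no figure of the plan's to reproduce. The check is a side-by-side reading, a date calculation and a look at whether the caudate scale matters.

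**1. Differences between Protocol 6.0 and the SAP**

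| Item | Protocol 6.0 | SAP 1.0 |
|---|---|---|
| Caudate volume (key secondary) | Change (2.7, 9.3.3.2) | Percent change (Table 1, 5.3); change in 1.3.2; no model of absolute change |
| Missing tHTT data | Imputation under missing not at random, plus tipping point with a shift parameter (9.6) | Control-based imputation and completers only (3.4.8, 5.2.2, Appendix I) |
| CSF mHTT, runs | No exclusion (9.3.3.2) | Run dropped if its baseline is at or below 2 × the lower limit of quantification, 3.44 pg/mL (5.3) |
| CSF mHTT, subjects | No exclusion (9.3.3.2) | Subject excluded if Month 12 differs from the Month 6 and 9 average by more than 40%; analysis with outliers becomes the sensitivity analysis (Table 1, 5.3) |
| Primary comparison | Nominal p value for each dose (9.3.3.1) | Fixed sequence, 10 mg then 5 mg (3.4.7) |
| mHTT at Month 12 | ANCOVA with dose and baseline, besides the repeated-measures model (9.3.3.2) | Repeated-measures model only (5.3) |
| cUHDRS | MMRM over visits (9.3.3.2) | ANCOVA at Month 12 (Table 1, 5.3) |

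The CSF sensitivity analysis restores the outlying subjects. The SAP does not say that it restores the dropped runs.

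**2. The cUHDRS change is forced.** The score in SAP 3.4.4 needs Stroop Word Reading. Protocol Table 4 schedules the full cognitive part on Day 1 and at Month 12, and SDMT alone at Visits 3 to 7. With one scheduled post-baseline score, a by-visit MMRM is in effect an ANCOVA. It is still a difference to list. So is the baseline cUHDRS covariate, which the protocol's model does not name.

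**3. Not counted as changes.** Protocol 9.3.1 allows transformation, so the log scale for tHTT is covered. Protocol 9.6 foresees control-based imputation. Protocol 9.1 groups the Safety Population by treatment received and is silent on subjects who received more than one; SAP 2.3 fills that gap.

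**4. Dates.** From 30 June 2024 to 17 March 2025 is 260 days, and 260 / 30.44 = 8.5 months. From 30 June 2023 it is 626 days, or 20.6 months. Protocol 6.0 (5 October 2023) is itself later than the June 2023 analysis, so June 2024 is the main reference point for differences from that version.

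**5. Does the caudate scale matter?** Percent change = 100 × change / baseline. For equal absolute loss, two subjects' percent changes stand in the inverse ratio of their baselines. The documents give no baseline spread. Assume a coefficient of variation of 15% to 25%. A subject one SD below the mean baseline then shows a percent loss 1.15 / 0.85 = 1.35 to 1.25 / 0.75 = 1.67 times that of a subject one SD above. Baseline volume as a covariate does not make the two scales equivalent.

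To see how often conclusions would differ, trials of 48 v 48 were simulated. That is 144 subjects split 72 and 72 between the 5 mg and 10 mg parts, then 48:24 within each, with placebo pooled to 24 + 24 = 48. Each scale was analysed by ANCOVA on treatment and baseline volume, with atrophy either proportional to baseline or additive. The two scales disagreed on p < 0.05 in roughly 1% to 3% of trials with no effect, and in roughly 5% to 10% with an effect of 0.4 SD.

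**The case against.** The strongest reply is that most of this is open, harmless or unavoidable.

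- **Slope comparison.** One might infer that it was dropped. It was not: SAP 5.3 has continuous time, a random intercept and slope, and a time-by-treatment term, which is the between-arm slope difference. Only the commitment to report it is missing.
- **Visibility of absolute caudate change.** SAP 3.4.3 and 5.3 provide for caudate volumes and volume changes to be reported, with volumes summarised by arm and visit. What is missing is the model-based comparison.
- **CSF rule.** SAP 5.3 gives its reason and plans the analysis with outliers included.
- **Fixed sequence.** It tightens error control.
- **Timing.** SAP section 1 places all decisions before database lock and unblinding.

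Each of these stands and narrows the point. None makes 3.5 true, because a well-reasoned change is still a change.

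A reader might go further and infer that interim results steered the caudate choice, or that the p value is biased. The documents do not support this. The interim summaries were descriptive and covered about 36 Stage 2 subjects (36 / 252 = 14% of maximum enrolment, or 36 / 144 = 25% of Parts A, B, D and E). SAP 3.3 does not name vMRI and says that subject-level blinding was kept. No section dates any decision, and only the CSF outlier rule cites interim data.

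Nor does an error-rate argument help. Picking the better scale on the final data would give 5.4% to 6.3% in the simulation instead of 5%, but section 1 rules that out. When the scale was chosen on interim data (12 v 12 assumed) and then tested at 48 v 48, the error rate was 4.7% to 5.2%, against 4.6% to 5.2% for a scale fixed in advance. Secondary p values are nominal in any case (SAP 3.4.7).

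**Conclusion.** SAP 3.5 is wrong as written. Seven differences from Protocol 6.0 are undeclared, and the cUHDRS move to ANCOVA is forced by the schedule. The two that matter most are the scale of the key secondary endpoint, on which the SAP also disagrees with itself, and the missing tipping-point analysis for the primary endpoint.

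The size is moderate. On the assumed baseline spread, absolute and percent change would usually lead to the same conclusion but would differ in about one trial in 20 to one in 10 at 0.4 SD. Those figures rest on a coefficient of variation that is not in the documents and on a single-visit ANCOVA in place of the planned random-slope model, so they are only a guide.

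The choices were fixed before the final unblinding, and are first documented after the interim summaries. That order is a reason to state when each was made. It is not evidence that interim results drove them.

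**What to change.** 1. Replace SAP 3.5 with a list of the seven differences. Give for each its reason and whether it was decided before or after the June 2024 summaries, and the June 2023 ones where relevant.
2. Make SAP 1.3.2 agree with 5.3 and Table 1 on the caudate variable.
3. Add two named supportive analyses: absolute change in caudate volume at Month 12 under the 5.3 model, and the tipping-point analysis for blood tHTT at Month 3.
4. State in 5.3 that the time-by-treatment (slope) contrast will be reported with its interval.

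The cost is SAP wording and a few extra model runs on data already collected, with no effect on conduct. The downside is that the report must label some analyses as changed from the protocol.
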